### Measure Standing Height

1. Ensure that the height board is on level ground.
2. Working with the mother, and kneeling in order to be at the level of the child:
  - a. Help the child stand on the baseboard with the weight of the child evenly distributed on both feet. The heels of the feet are placed together with both heels touching the base of the vertical board. Place the feet pointed slightly outward at a 60 degree angle.
  - b. The back of the head, shoulder blades, buttocks, calves, and heels should all touch the vertical board. Arms should hang freely by the sides of the body with the palms facing the thighs. **Note: Standing with all body parts touching the board may be difficult for some children, in which case, help the child to stand on the board with one or more contact points touching the board.**
  - c. Ask the mother to hold the child's knees and ankles to help keep the legs straight and feet flat, with heels and calves touching the vertical board. Ask her to focus the child's attention, soothe the child as needed, and inform you if the child moves out of position.
  - d. Position the child's head so that a horizontal line from the ear canal to the lower border of the eye socket runs parallel to the baseboard.
  - e. Ask the child to inhale deeply and to stand fully erect without altering the position of the heels. If necessary, push gently on the belly to help the child stand to full height.
  - f. Still keeping the head in position, use your other hand to pull down the headboard to rest firmly on top of the head and compress the hair.
3. **Upon reading the measurement, the examiner will clearly call out the number to the recorder.** Record the child's height in centimeters to the last completed 0.1 cm (1.0 mm).
4. Keeping the child in place, release the sliding headboard, and prepare to repeat the measurement. Re-position the child for a second and third measurement.

### Dismantling the ShorrBoard

- 1) Stand the board upright: face the board and step on the base with one foot to keep it stable.
- 2) Slide the head/footpiece into the base of the main board.
- 3) Release the clasp on the back of the extension piece and remove it. Push the clasp FLAT against the extension piece.
- 4) To attach the extension piece to the main board, turn the front of the extension piece inward and place it against the front of the main board. Make sure that all sides of the extension piece are straight and in line with the main board.
- 5) Push on the bolt that is on the back of the extension piece and screw it into the main board.
- 6) Put the board back inside of the carrying case for storage until your next use.

### Measuring Weight

The SECA 874 scale will be used to weigh infants and children to the nearest 0.1 kg. Infants and young children can also be weighed simultaneously with their parent or guardian by the unique “mother-baby” function (parent or guardian is weighed and then the infant or child is weighed while held by the parent).

Explain to the mother that we want to weigh her child to see how he or she is growing. If she has a baby or a child who is unable to stand, she will hold the child on the scale. If the child is 2 years or older/can stand alone, the child will be weighed alone.

Children should be wearing only light clothing, no shoes or sandals, no hair ornaments, and no jewelry. Explain that the child needs to remove outer clothing and shoes/sandals in order to obtain an accurate weight. If the baby is wearing a diaper, the diaper should be removed. If any heavy clothes remain on the child, make a note in the *Notes* section.

### Seca 874 Scale

- 1) Remove scale from bag.
- 2) Be sure that the scale is placed on a flat, hard, even surface. All 4 legs of the scale should make contact with the ground surface, without wobbling. It may be helpful to place a piece of plywood on the ground underneath the scale.
- 3) When **batt** appears in the display, you should change the batteries. Remove the old batteries and insert 6 new batteries.

Turn the power on the scale when you are ready to begin weighing.

1. **If the child is unable to stand on the scale**, you will use the 2 in 1 weighing function (called *tared* weighing). The **2 in 1** function enables the weight of babies and small children to be determined while an adult holds them.
  - a. Identify a suitable area that is flat for horizontal placement of the scale.
  - b. Press the start key with no load on the scale. The scale is ready for use when it sets to 0.00.
    - i. If necessary, switch the weight display to KG: hold down the 2 in 1 key for about 3 seconds. Press the start key with no load on the scale. Wait until the display shows 0.00.

- c. Ask the adult to remove his/her shoes and stand in the middle of the scale without the child. S/he should remove any long garments, as these can cover the display and also lead to variable measurements.
  - d. After the adult's weight appears on the display, tell him/her to remain standing on the scale. Press the **2 in 1** key to activate the function.
  - e. The scale stores the weight of the adult and the display returns to zero. When 0.00 and NET appear in the display, hand the child to the adult. The scale will determine the weight of the child. Once the value is stable for about 3 seconds, the weight is measured.
    - i. Note: If an adult is very heavy (e.g. more than 100 kg) and the baby's weight is relatively low (e.g. less than 2.5 kg), the baby's weight may not register on the scale. In such cases, have a lighter person hold the baby on the scale.
  - f. **The positioner will clearly call out the child's weight to the recorder.**
  - g. Record the child's weight to the nearest 0.01 kg.
  - h. Repeat the measurement 2 more times. Note that only the baby needs to be removed from the scale; the adult should remain on the scale the entire time.
  - i. To turn off the **2 in 1** function, press the **2 in 1** key. The **2 in 1** function remains on until you press the **2 in 1** key again, or until the scale switches off automatically.
2. **If the child is able to stand on the scale**, you will weigh the child alone. Talk with the child about the need to stand still. Communicate with the child in a sensitive, non-frightening way.
- a. Press the start key with no load on the scale. The scale is ready for use when it sets to 0.00.
  - b. Ask the child to stand in the middle of the scale. Once on the scale, the child must stand still. The HOLD function is automatically activated for weights over 1.5 kg/3.3 lbs. The display flashes until a stable weight has been measured. The display is then frozen until the next weighing operation.
    - i. Note: If the child jumps on the scale or won't stand still, you will need to use the tared weighing procedure instead.
  - c. **The positioner will clearly call out the child's weight to the recorder.** Record the child's weight to the nearest 0.01 kg.
  - d. Repeat the measurement 2 more times. Have the child move completely off the scale and then stand again on the scale.

If no further weighing operations are performed, the scale switches off automatically after 2-3 minutes.

[figure not shown]
[figure not shown]
#### **Scale Calibration**

In order to monitor the calibration of the scales over time, each team will weigh a 5 kg test weight at the beginning and end of the day.

### **Measuring Mid-Upper Arm Circumference (MUAC)**

The child's MUAC will be measured **three times**. MUAC measurements will be taken at the midpoint of the **left** arm between the tip of the shoulder and the tip of the elbow using non-stretch MUAC tapes.

1. First, **find the approximate midpoint of the upper arm**. Have the child stand up straight with feet together, and the right arm bent 90 degrees at the elbow, palm facing up. The examiner is positioned behind the child. If it is helpful, mark the midpoint with a permanent marker.
2. To **measure mid-upper arm circumference**, have the child stand up straight with the arms relaxed at the sides. The examiner will stand facing the child's right side. The measuring tape is placed around the upper arm at the marked point.
3. Wrap the tape around the arm, pulling it to lie flat against the surface of the skin. Be careful not to pull the tape too tightly (to compress the skin).
4. The line for reading measurements is clearly labeled on the MUAC tape (READ (cm)). Read the number aligned with the measurement line on the tape. **Upon measuring, the examiner will clearly call out the number to the recorder.** Record to the nearest 0.1 cm (0.1 cm = 1 mm).
5. Keeping the child in place, release the MUAC strip.

### 3.3. Malaria Rapid Diagnostic Test

[figure not shown]
Malaria infection status will be assessed on all enrolled children using a rapid diagnostic test (RDT) at baseline and 8 weeks after admission into the nutritional program. At this point, we will also take the child's temperature.

#### Supplies

[figure not shown]
- Mobile data collection device & accessories
- RDT test packet
- Alcohol swabs
- Gloves
- Lancet
- Buffer
- Timer

#### Conduct the Malaria RDT

1. Check the expiry date on the test packet. If the expiry date has passed, choose another packet that has not yet expired.
2. Put on the gloves. Use new gloves for each patient.
3. Open the packet and remove:
  - a. The test
  - b. The capillary tube
  - c. The desiccant sachet
4. Write the patient's name and study ID number on the test
5. Open the alcohol swab. Grasp the 4th finger on the patient's left hand. Clean the finger with the alcohol swab. Allow the finger to dry before pricking.
6. Open the lancet. Prick patient's finger to get a drop of blood.
7. Discard the lancet into an appropriate sharps receptacle immediately after pricking the finger.
8. Use the capillary tube to collect the drop of blood.
9. Use the capillary tube to put the drop of blood into the square hole on the test marked "A."
10. Discard the capillary tube into an appropriate sharps receptacle
11. Add 6 drops of buffer into the round hole marked "B."
12. Wait 15 minutes after adding buffer
13. Read test results. Do NOT read the test sooner than 15 minutes after adding the buffer. You may get false results
14. How to read the test results:
  - a. POSITIVE: a line near letter "C" and a line near letter "T" means the patient is positive for malaria.

[figure not shown]

- i. The test is positive even if the line near "T" is faint

[figure not shown]
*P. falciparum* (faint +)

- b. **NEGATIVE:** a line near letter “C” and NO LINE near letter “T” means the patient does NOT have malaria

Negative

- c. **INVALID RESULT:** NO LINE near letter “C” and one or no line near letter “T” means the test is INVALID

- i. Repeat the test using a new RDT and a new lancet if no control line appears

15. Dispose of gloves, alcohol swab, desiccant sachet, and packaging  
16. Record the test result in the mobile application.

### 3.4. Rectal swab collection

Rectal swabs will be collected at baseline and at week 8 in a random subset of children.

#### Procedure

The test will require that the child’s parent and examiners work together to obtain a good sample. Is it important to describe the test to the parent so that they can best assist with keeping the child still during the procedure.

Rectal swabs can be collected in the following way:

1. Put on a clean pair of gloves.
2. Partially open the fecal swab package and remove the top section of the collection vial (this can be discarded).
3. Position the child:
  - Lie the child on his/her back, hold legs in the air (it is useful to have assistance).
  - Or have the child lay on his/her stomach across the mother/guardian’s lap
4. Remove the swab from the package. Take care that the cotton tip is not touched. If it is touched, throw the swab away and begin with a new one.

5. Insert the tip of the swab into the child's anus only as far as needed to contact fecal material (1-3cm) and rotate 180 degrees. The tip should be a brownish color when removed.
6. Place swab into the preservative in the collection tube. Make sure the swab is fully submerged in the liquid preservative and then break the swab off using the pre-scored breaking point.
7. Screw the cap back on the tube and make sure that it's tightened. Wrap the area where the cap meets the tube with Parafilm to ensure that the sample will not leak, and then place the tube into the appropriate sample box.
  - If the swab cannot be broken off while the tip is fully submerged in the liquid, try twirling the swab in the liquid first (to release the contents of the sample into the preservative) before breaking it off. Avoid rubbing the sample on the tip of the swab off on the side of the tube where there is no liquid.
8. Place a random number label on the collection tube.
9. Place the tube the rectal swab container.
10. Swab storage for Genetic analysis: Store samples at room temperature. According to the manufacturer, the preservative in the tube will preserve DNA for 5 months at room temperature (7 days for RNA), and thereafter can be frozen (-20°C or -80°C) for long-term storage.

### Materials for Rectal Swab Collection

#### Swab

An individually-wrapped Copan flocked swab with a plastic shaft will be used to collect the rectal swab and then placed into a Zymo transport medium.

#### Sample Tube with Media

The specimen will be in a sterile Stool Nucleic Acid Collection and Transport Tube containing Zymo research Transport Medium with a cap that will be tightened firmly.

### **3.5. Vital Status**

Vital status will be recorded at all follow-up visits, including whether the child is alive, has died, or has moved. Date of death and location of move will be recorded.

### **3.6. Clinical examination**

Outcomes of clinical examinations will be collected at enrollment, weekly follow-up visits, and at week 8. Clinical examinations will be conducted according to the standard of care in the management of SAM. Recorded outcomes include diagnoses made and treatments given/recommended.

#### **4. STUDY MEDICATION**

Children enrolled in the study will be offered weight-based, directly observed, oral suspension azithromycin or a short course of oral amoxicillin. We will monitor adverse events following treatment as described in Section 5.

##### **Study Medication Description**

Zithromax® for oral suspension is supplied in bottles containing azithromycin dehydrate powder equivalent to 1200mg per bottle and the following inactive ingredients: sucrose; tribasic anhydrous sodium phosphate; hydroxypropyl cellulose; xanthan gum; FD&C Red #40; and flavoring including spray dried artificial cherry, crème de vanilla, and banana. After constitution, a 5mL suspension contains 200mg of azithromycin.

The oral amoxicillin routinely used at each CSPA for treatment of uncomplicated severe acute malnutrition will be used for this trial.

##### **Dosage Information**

Azithromycin will be administered as a single dose, in oral suspension form for children. Dosing will follow the WHO recommendations for treatment of active trachoma:

- Single dose of 20mg/kg in children (up to the maximum adult dose of 1g)

Individuals who are allergic to macrolides/azalides will not be treated.

Oral amoxicillin (80 mg per kilogram of body weight per day, divided into two daily doses) will be administered for 7 days. The first dose will be administered by the study nurse, who will teach the caregiver how to administer the medication at home. The remaining doses will be administered by the caregiver.

##### **Medication Procurement**

Azithromycin and amoxicillin will be purchased locally in Burkina Faso by the study team. Enrolled participants will incur no costs associated with the study medication.

##### **Medication Quality Control**

Study medication will be stored at each site prior to use. The CRSN study team and site staff will regularly check and record the study medication expiration dates. The expiration dates on the medication containers will be strictly monitored and all expired study medicine will be discarded appropriately. The study coordinator will work with each health facility to ensure that they have appropriate stock of all study medications.

## 5. ADVERSE EVENTS

Parents or guardians of enrolled children will be instructed to report any adverse events experienced within the 7 days following the enrollment visit, by phone or in person. At all follow-up visits, study staff will inquire about the child's experience of adverse events, including if the child had any of the following symptoms:

- Fever
- Diarrhea
- Vomiting
- Abdominal pain
- Skin rash
- Constipation

The study team will assess whether the parent or guardian sought care for the child since the last visit and if so, what the reason was for the health care visit and if the child was hospitalized.

Serious adverse events will be defined as death, hospitalization, or any other life-threatening situation. Serious adverse events will be reported to the Medical Monitor within 24 hours. The study team member conducting the follow-up visit will email the CRSN Principal Investigator, who will immediately email the Medical Monitor and the UCSF study team. The Medical Monitor will make a determination as to whether the event could be reasonably considered to be related to the study drug and will report the results of this determination to the study investigators and the DSMC as needed. Information on all adverse events, serious and non-serious, will be recorded on data collection forms through the mobile application.

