### Secondary Outcomes

- **Nutritional recovery by 8 weeks (Specific Aim 2).** Nutritional recovery will be defined as a child having WHZ  $\geq -2$  on two consecutive visits and no acute complication or edema for the past 7 days OR MUAC of  $\geq 125$ mm on 2 consecutive visits and no acute complication or edema for the past 7 days. The criteria chosen to define the recovery will be the same one we used to admit the child into the program.

- **Time to recovery.** Time from enrollment to nutritional recovery (defined above) will be calculated in days by subtracting the date of enrollment from the date of nutritional recovery.
- **Nonresponse at 8 weeks.** Nonresponse will be documented if a child does not meet the criteria for nutritional recovery at 8 weeks.
- **Transfer to inpatient care.** The occurrence, date, and reason for transfer from outpatient to inpatient treatment will be recorded.
- **Mortality by 8 weeks.** Vital status will be assessed at all follow-up time points and mortality will be defined as death during the study period. Date of death will be recorded.
- **Clinical signs of infection.** At all follow-up time points, clinical signs of infection will be recorded, including care-giver reported experience of fever, diarrhea, vomiting, and respiratory infection/cough and clinical diagnoses made at by site personnel
- **Adverse events.** Adverse events will be reported at all follow-up time points (defined in Section 5).
- **HAZ.** Height or length will be measured at all follow-up time points and height-for-age z-scores will be calculated.
- **MUAC.** Mid-upper arm circumference will be measured at all follow-up time points.
- **WAZ.** Weight will be measured at all follow-up time points and weight-for-age z-scores will be calculated.
- **WHZ.** Weight and height, assessed at all follow-up time points, will be used to calculate weight-for-height z-scores.
- **Malaria.** Rapid diagnostic tests for malaria will be conducted at baseline and week 8 to determine malaria infection status.
- **Intestinal microbiome:** Rectal swabs will be collected in a random subset of children at baseline and at week 8.

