## **6. DATA COLLECTION, MANAGEMENT, AND SECURITY**

### **6.1. Data Collection**

Data will be collected on enrolled children at baseline (time of enrollment), and follow-up weeks 1- 8. Written informed consent will be collected on paper and the study nurse will record treatment administration on paper. All other data will be collected electronically on mobile devices using the Interviewer mobile application by Survey Solutions. Data to be collected are outlined in Figure 1 and Section 2.5.

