### **Secondary outcomes.**

Time to event outcomes (time to recovery and time to mortality) will be assessed visually using Kaplan-Meier curves and compared by arm using the log-rank test.

Binary outcomes will be analyzed using modified Poisson regression for rare outcomes (e.g. mortality) or log-binomial regression for common outcomes (e.g. malaria), using models similar to the one described above for Specific Aim 2.

Anthropometric assessments will be analyzed using linear models as described for Specific Aim 1, with correction for baseline values. For anthropometric assessments, z-scores will be calculated based on the 2006 WHO Child Growth Standards. Anthropometric z-scores will be analyzed as continuous variables and secondary analyses will explore categorization.

All analyses will be intention-to-treat. A significance level of 0.05 for inference and 95% confidence intervals will be reported for all effect estimates. All analyses will be conducted using R (R Foundation for Statistical Computing, Vienna, Austria). For all models, model diagnostics will be conducted to assess appropriate fit.

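### Fever, diarrhea and vomiting feed both the infection and the adverse-event outcomes, and no early window is set for the adverse-event comparison, so an acute drug reaction could be diluted

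*Combined protocol and SAP*

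**What the plan says.** Section 2.5 (Secondary Outcomes) lists clinical signs of infection and adverse events as two separate outcomes.

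- **Infection:** "At all follow-up time points, clinical signs of infection will be recorded, including care-giver reported experience of fever, diarrhea, vomiting, and respiratory infection/cough". Diagnoses made by site staff are added to these.
- **Adverse events:** reported at every follow-up time point, with the definition left to Section 5.

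Section 5 then says: "At all follow-up visits, study staff will inquire about the child's experience of adverse events, including if the child had any of the following symptoms". The list is fever, diarrhea, vomiting, abdominal pain, skin rash and constipation. The only early window is an instruction to caregivers, who "will be instructed to report any adverse events experienced within the 7 days following the enrollment visit". Relatedness is described for serious events only: "The Medical Monitor will make a determination as to whether the event could be reasonably considered to be related to the study drug".

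Section 9.2 does not name adverse events. Its general rule is "Binary outcomes will be analyzed using modified Poisson regression for rare outcomes", with log-binomial regression for common outcomes, on models like the one for Specific Aim 2. That model has one result per child by 8 weeks.

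Section 2.3 says that participants are not masked. Under Section 4 (Dosage Information), azithromycin is a single dose and amoxicillin runs for 7 days, mostly given by the caregiver at home.

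**The concern.** The same informants report the same three symptoms at the same visits for two outcomes. Nothing says when such a symptom counts as a possible drug reaction and when as an intercurrent infection. For non-serious events no relatedness judgement separates the two.

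A reaction to a single dose or a 7-day course would be expected mainly early, whereas childhood fever and diarrhea continue throughout follow-up. If both go into one ever/never variable, a child who vomits on the day of dosing and a child with fever in week 6 count the same. A real early difference between the drugs could then be reported as no difference, although visit-level data could show it. Leaving the window open also means that it could be chosen after the data are seen.

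**Working it through.** **Overlap of the two definitions**

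| Item | Infection outcome (2.5) | Adverse events (5) |
|---|---|---|
| Fever, diarrhea, vomiting | yes | yes |
| Respiratory infection/cough, site diagnoses | yes | not listed |
| Abdominal pain, skin rash, constipation | not listed | yes |
| Time points | all follow-up | all follow-up |
| Relatedness judged | no | serious events only |

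The overlap is three of the six solicited symptoms.

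**Inputs.** Section 9.1 gives 300 children, 1:1, with 10% loss: 300 × 0.9 = 270, or 135 per arm. Alpha is 0.05, taken as two-sided. The plan gives no symptom rates and no power for adverse events, so there is no stated figure to reproduce and all rates below are assumptions. The power formula is the normal approximation for two proportions. As a check, it returns 80.1% for Specific Aim 2 (66% v 81%, 135 per arm), against the stated 80%.

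**Model 1.** Weekly risk *p* of any listed symptom in both arms, doubled to 2*p* in week 1 in one arm, with every child seen in all 8 weeks.

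- Control over 8 weeks: 1 − (1 − *p*)^8
- Other arm over 8 weeks: 1 − (1 − 2*p*)(1 − *p*)^7
- Difference in week 1: *p*. Difference over 8 weeks: *p*(1 − *p*)^7

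Pooling therefore multiplies the week-1 difference by (1 − *p*)^7, the share of children with no later symptom. At *p* = 0.15 this is 0.85^7 = 0.32. The 8-week risks are 1 − 0.85^8 = 72.8% and 1 − 0.70 × 0.3206 = 77.6%, a risk ratio of 1.07.

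| Weekly background | Week 1 | Power, week 1 | 8 weeks, ever/never | Power, 8 weeks |
|---|---|---|---|---|
| 15% | 30% v 15% | 84% | 77.6% v 72.8% | 15% |
| 10% | 20% v 10% | 63% | 61.7% v 57.0% | 12-13% |
| 5% | 10% v 5% | 34% | 37.1% v 33.7% | 9% |
| 2% | 4% v 2% | 16% | 16.7% v 14.9% | 6-7% |

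The ranges reflect variants of the normal approximation.

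**Model 2.** A one-off week-1 reaction risk of 15% v 5%, on top of an equal weekly background *b*. The difference is 0.10(1 − *b*) in week 1 and 0.10(1 − *b*)^8 over 8 weeks.

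| Background | Week-1 difference (power) | 8-week difference (power) |
|---|---|---|
| 2% | 9.8 points (71%) | 8.5 points (38%) |
| 5% | 9.5 points (60%) | 6.6 points (20%) |
| 10% | 9.0 points (47%) | 4.3 points (11%) |

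**Cancellation.** This needs a further assumption: less later illness in the arm with more reactions. With later symptoms 20% lower, Model 1 at 15% gives 71.4% v 72.8% (risk ratio 0.98). With background illness 20% lower, Model 2 gives 8-week differences of 6.1, 1.7 and −2.7 points at 2%, 5% and 10%, while the week-1 differences are 9.5, 8.7 and 7.3 points.

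**The case against.** The strongest reply is that the plan leaves the adverse-event analysis open; it does not prescribe a bad one. Section 9.2 never says that adverse events will be reduced to ever/never over 8 weeks. Symptoms are asked about at each visit and early events can be reported separately, so a by-week presentation fits the text too. This stands. A reader might infer that acute reactions will be diluted or cancelled, but dilution is conditional on pooling. Cancellation also needs unequal later illness, for which the documents give no data.

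Three other stronger readings are tempting and also fail:

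- *The adverse-event comparison merely repeats the infection comparison.* Each outcome has components that the other lacks, and serious events receive a relatedness judgement.
- *The quarterly committee reports share the problem.* Section 6.3 promises aggregate adverse-event data without saying by arm, by window or in what form.
- *An early window gives the trial good power for each symptom.* The 84% belongs to a composite at a 15% weekly background. A single symptom would be rarer, and at 2% to 5% week-1 power is only 16% to 34%.

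It is also fair to say that recording all adverse events whatever their cause is legitimate, and that moving every later fever or vomiting episode out of that outcome would be debatable. Amoxicillin runs for 7 days, so a days 0-7 window leaves little time after the course. The early window also relies on caregivers who know the treatment.

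What the reply does not remove is the shared symptoms, the missing attribution rule for non-serious events, and the absence of any analysis that uses the plan's own 7-day window.

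**Conclusion.** The point holds as a cheap improvement to secondary outcomes of a pilot trial. The plan does not separate infection symptoms from possible drug reactions and pre-specifies no early adverse-event comparison. If events are pooled over follow-up, a week-1 difference shrinks at every rate tried: to about a third of its size at a 15% weekly background, but to 87% of its size (0.98^7) at 2%. Power falls from 84% to 15% in the first case and from 16% to 6-7% in the second.

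These sizes rest on assumed rates, independence between weeks, equal background illness in the arms and complete weekly observation. The last is not assured. Section 6.1 says "Data will be collected on enrolled children at baseline (time of enrollment), and follow-up weeks 1- 8", while Section 2.4 ends weekly visits at recovery and resumes at week 8. The week-1 visit is less exposed to this: recovery needs two consecutive qualifying visits on the criterion used for admission, so no child can meet it before the second follow-up visit.

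**What to change.** In Sections 2.5, 5 and 9.2:

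1. Pre-specify, as the acute tolerability comparison, the proportion of children in each arm with each solicited symptom reported for days 0-7 (week-1 visit plus caregiver reports), with risk ratios and 95% confidence intervals. Say that power for single symptoms is low and that the intervals are the result to read.
2. Tabulate each solicited symptom by week and arm alongside it, so that events soon after the 7-day amoxicillin course remain visible.
3. Keep all adverse events and serious adverse events over the full 8 weeks.
4. State that later fever, diarrhea and vomiting overlap with clinical signs of infection, and that the two outcomes are not independent evidence.
5. State the recall period for the symptom questions.

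The cost is wording and one extra pre-specified table, with no change to treatment or visits. Sections 5 and 6.1 indicate that symptoms are collected by visit. The study forms (Appendix 2) are not in the reviewed text, so it should be confirmed that they record each symptom by visit. The early comparison remains open to reporting bias from unmasked caregivers, and the write-up should say so.
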